VIII. Risks**VIII.1** *What are the risks to subjects including*

- *emotional or psychological*
- *financial*
- *legal or social*
- *physical?*

tDCS safety: tDCS is a non-invasive brain stimulation technique in which a very weak electrical current is applied to the scalp. tDCS has been conducted on humans and animals for many years and no evidence has emerged to suggest that it is harmful or has ever induced a serious side effect. However, the safety of tDCS is dependent on current strength, electrode size, and stimulation duration. Accordingly, these parameters have been investigated to establish safe and effective stimulation parameters for tDCS applications in research involving human subjects. The only side effects that have been reported when proper guidelines are followed are a temporary headache, skin redness under the electrodes, and/or tingling, itching, and burning sensations in some subjects. For example, a 2008 review of the approximately 100 human tDCS studies up until that time on healthy adults and patients found that 64 of these studies reported no side effects, 24 studies reported a temporary itching or tingling under the electrodes in some subjects, and one study reported skin redness. Furthermore, these slight side effects were of equal occurrence in subjects that received placebo stimulation in 7 studies. In addition, only two subjects in these 100 studies reported a mild headache. Similar findings have recently been reported in research and review articles (Nitsche et al. 2008; Hummel et al. 2008). Physiological studies have also assessed the safety of tDCS when applied within the aforementioned stimulation guidelines. For example, there was no neuronal damage as measured by serum neuron-specific enolase (Stagg & Nitsche, 2011) or MRI measures of edema using contrast enhanced and diffusion-weighted MRI measures following administration of tDCS (Nitsche et al. 2004). Furthermore, tDCS did not negatively alter measures of neuropsychological function and EEG activity (Iver et al. 2005). Accordingly, rat studies using tDCS models emulating tDCS applied to humans (Liebetanz et al. 2009) showed that the current density needed to induce tissue damage or lesions was about 1429 mA/cm², whereas the current densities used in human studies are between 0.04 and 0.08 mA/cm² and in this proposal are 0.06 mA/cm² and 0.011 mA/cm². In conclusion, the tDCS stimulation parameters in this study are identical to the most common in the literature and have been proven to be exceptionally safe and well-tolerated. The probability is very unlikely that harm may occur (see above). Based on the available literature a slight headache should be the worst possible negative effect and should be very rare. In this case, non-prescription medication should relieve the headache within 1-2 hours.

Risks of performing motor tasks: There is potential for injury (muscle strain) resulting from the walking and balance tests and training. There is also a potential for falling during the balance tasks, particularly for PwMS, who have a higher fall risk in general. Other risks may include feelings of anxiety and/or stress induced by the experiment, which can lead to an increase in heart rate and blood pressure.

PET Imaging: This study involves the administration of a PET radiopharmaceutical, [18F]fluorodeoxyglucose (FDG). FDG has been used at the University of Iowa and throughout the world for a variety of conditions. There have been a few reports of relatively rare side-effects involving temporary low blood pressure and allergic reactions. As a result of participating in this research, each subject will receive a dose of radiation equivalent to approximately 90% of the dose that a medical radiation worker can accrue yearly. Although there are no proven harmful effects from the level of radiation exposure in this study, long-term effects on a subject's health cannot be ruled out with certainty. Pregnancy is a contraindication to PET imaging. Thus, all women of childbearing potential will undergo a pregnancy test before PET imaging. Injection of tracers will require the placement of an intravenous catheter. As in any procedures involving catheters placed in veins, there are several risks, including infection, clotting, or continued bleeding. There may also be bruising, skin irritation, and a dull ache at the site of injection. The subject will be asked to fast for a minimum of 6 hours

prior to the FDG study. There is a small risk of hypoglycemia associated with this fast.

Risks of MRI: Participants may be uncomfortable inside the MRI scanner if they do not like to be in closed spaces (“claustrophobia”). During the procedure, they will be able to talk with the MRI staff through a speaker system. Participants can stop the scan at any time.

The MRI scanner produces a loud hammering noise, which has produced hearing loss in a very small number of patients. Participants will be given noise-canceling headphones to reduce this risk. A metal object flying through the air toward the magnet and hitting the participants presents the greatest risk associated with MRI. To reduce this risk, we require that all people involved with the study remove all metal from their clothing and pockets. No metal objects will be brought into the magnet room while participants are inside the room. In addition, the door to the room will remain closed throughout the study so that no one can accidentally bring a metal object into the room.

There are no known risks associated with limited exposure to magnetic fields. Magnets of this strength have been in use for medical imaging for over 15 years. However, we will keep a record of the length of time participants were in the magnet, as well as the amount of radio waves used during that time.

Although the risk is minimal, there is a risk for breach of confidentiality.

VIII.2

What have you done to minimize the risks?

- *If applicable to this study ALSO include:*
 - *How you (members of your research team at Iowa) will monitor the safety of individual subjects.*
 - *Include a description of the availability of medical or psychological resources that subjects might require as a consequence of participating in this research and how referral will occur if necessary (e.g. availability of emergency medical care, psychological counseling, etc.)*

All risks will be minimized by using safe, well-established procedures and strict monitoring of each experimental session. Study staff will be in close proximity to each subject to help prevent/minimize fall risk and muscle strain. Furthermore, risk will be minimized by using stimulation parameters that are well described, within international guidelines, and within the range of those used in hundreds, if not thousands, of studies (see above).

The venous catheter will be inserted by an individual from the PET Center that is qualified, trained, and experienced at inserting venous lines.

Because the subject will be asked to fast for a minimum of 6 hours, there is a small risk of hypoglycemia. Prior to the injection of FDG, the blood glucose level will be checked. If the subject is found to be hypoglycemic at that time, glucose will be administered orally (e.g., juice) or by IV depending on the subject's level and symptoms.

VIII.3

Does this study have a plan to have an individual or committee review combined data from all subjects on a periodic basis (such as summary or aggregate safety and/or efficacy data)?

No

IX. Benefits

IX.1

What are the direct benefits to the subject (do not include compensation or hypothesized results)?

There is no personal benefit associated with this protocol.

IX.2

What are the potential benefits to society in terms of knowledge to be gained as a result of this project?

The outcomes may help to improve rehabilitative procedures for people with MS who have gait or balance impairments.

X. Privacy & Confidentiality

X.1

What are you doing to protect the *privacy* interests of the subjects?

Subjects will be consented in a private room (i.e., room N414 of the Field House) or during a phone call at a time where the subject is comfortable discussing screening questions. During data collection, we will only collect the minimum amount of information necessary to answer the research question.

X.2*Are you collecting the Social Security Number of any subjects for any purpose?*

Yes

X.3*Provide the intended usage of SSN:*

- To provide compensation to subjects

X.4*How will information/data be collected and stored for this study (check all that apply):*

- Electronic records (computer files, electronic databases, etc.) - All data collected, including personal identifiable information, will be stored electronically on University of Iowa secured networks, with access restricted to the current investigators.
 - Name - [name]
 - Title - IT Support Consultant
 - University Job Classification - Faculty/Staff
- Paper/hard copy records (hard copy surveys, questionnaires, case report forms, pictures, etc.) - Hard copy data will be stored in a locked file cabinet accessible only by research personnel. At night, the second story of the Health and Human Physiology Department is restricted to authorized key holders, and the room in which the file cabinet is located is restricted to only current laboratory staff.

X.5*Do the confidentiality protections indicated above allow only members of the research team to access the data/specimens?*

Yes

X.7*Does your study meet the NIH criteria for a Certificate of Confidentiality or will you be applying for Certificate of Confidentiality?*

No

XI. Data Analysis

XI.1*Describe the analysis methods you will use, including, if applicable, the variables you will analyze*

All imaging data will be transferred to the Integrative Neurophysiology Lab in the Department of Health and Human Physiology for analysis. The prior and post-treatment FDG images will be co-registered to the anatomical CT images. Anatomically based volumes-of-interest (VOIs) will be generated manually using the View tool of PMOD. In the upper leg, the knee extensors (rectus femoris, vastus medialis, vastus intermedius, and vastus lateralis) and knee flexors (long and short head of the biceps femoris, semimembranosus, semitendinosus, sartorius, and gracilis) will be identified. In the lower leg, the plantar flexors (gastrocnemius, soleus, peroneus longus, peroneus brevis, flexor digitorum longus, flexor hallucis longus, and tibialis posterior) and the dorsiflexors (tibialis anterior, extensor digitorum longus, and extensor hallucis longus) will be identified. Standardized uptake values (SUV) based on the injected dose and body weight will be calculated for each muscle. Although the participants will fast for a minimum of 6 hours to minimize the impact of endogenous glucose and insulin, SUVs may be affected by blood glucose and insulin levels. Therefore, the SUV data will be analyzed without normalization and, separately, as values normalized to standard blood glucose (adjusted to 100 mg/dL) and/or by using the liver as a reference tissue to allow for comparison across experimental sessions. The data will be analyzed using PMOD Version 4.001 (PMD Technologies LLC, Zürich, Switzerland). Asymmetry indices (AIs) will be calculated to determine the magnitude of asymmetry in SUVs between the legs using a previously used equation^{23,82}. An AI greater than 10% will be considered asymmetric. Spearman's correlation will be used to test whether the change in FDG uptake is significantly related to the change in walking and balance scores after ctDCS and training. We will use a liberal significance threshold to avoid type II errors because the relatively low number of subjects in this study leads to conservative testing. The level of statistical significance for all brain imaging analyses is $p < 0.005$ without correction.

A stimulation (sham vs. 4 mA) by training (balance vs. gait) by time (24 hours, 2 weeks, and 4 weeks) ANCOVA with baseline measurements as covariates will be conducted on each outcome variable (e.g., distance walked on the 6MWT and FGA score) to compare the short- and long-term effects of gait and balance training combined with ctDCS. Levene's test and normality tests (QQ plots, Shapiro Wilk test, and histograms) will be used to test the statistical assumptions. Post-hoc testing (paired and unpaired t-tests) and effect sizes (Cohen's d) will be calculated to clarify significant main or interaction effects. Significance will be accepted at $p < 0.05$ and adjusted with a Bonferroni correction. Statistical analyses will be performed using SPSS 27 (IBM Corp, Armonk, NY, USA).

XI.2*Provide the rationale or power analysis to support the number of subjects proposed to complete this study.*

We used effect sizes (Cohen's $d = 2.08$ and 1.37 , respectively) from Pilloni et al. 202060 and Hebert et al. 201146 to calculate the required sample size. With a significance fixed at $p = 0.05$ and 80% power, we will require 40 total subjects ($n = 10$ in each group) to properly power the hypothesis test for a statistically significant change. Based on this calculation and the assumption of a standard drop out rate of approximately 20%, we propose to recruit 48 total subjects ($n = 12$ in each group).

XII. Future Research

XII.1 *Do you wish to keep any information about subjects involved with this research project so that members of the current research team may contact them in the future for your own research projects?*
Yes

XII.2 *Do you wish to keep any information about subjects involved with this research project so that other researchers may contact them for future research?*
Yes

XII.3 *List the data or information you will keep:*
Contact information and outcome of the phone questionnaire.

XII.4 *Does this project involve storing any data, tissues or specimens for future research?*
Yes – contribution for future use is mandatory for participation in the study

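### The FDG–function Spearman correlation has no term for randomised arm, so arm differences alone can make it significant, and the alpha rule that governs it is unclear

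*Combined protocol and SAP*

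**What the plan says.** The imaging paragraph of section XI.1 calculates an SUV for each listed leg muscle, in up to three versions (unnormalised, glucose-normalised, liver-referenced), and asymmetry indices between the legs. It then states that Spearman's "correlation will be used to test whether the change in FDG uptake is significantly related to the change in walking and balance scores"; the closing part of that sentence reads in full "related to the change in walking and balance scores after ctDCS and training". No covariate, stratification, primary FDG variable, primary functional score or number of correlations is given.

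Two threshold statements follow in the same section:

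- Imaging paragraph: "We will use a liberal significance threshold to avoid type II errors", and then "The level of statistical significance for all brain imaging analyses is $p < 0.005$ without correction".
- End of the ANCOVA paragraph: "Significance will be accepted at $p < 0.05$ and adjusted with a Bonferroni correction".

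The ANCOVA itself models stimulation, training and time, but it does not contain the correlation. Section I.5 expects gait, balance and uptake symmetry all to improve more with tDCS than with sham, and expects the largest gains with gait training plus tDCS.

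**The concern.** This is the only analysis in the plan that links muscle glucose uptake to function. A reader will want to know whether participants whose uptake changed more also improved more. A correlation across arms mixes that question with a second one: whether the arms differ on both measures. If stimulation moves both, as the trial hopes, active participants lie towards one corner of the scatterplot and sham participants towards the other. The pooled correlation is then non-zero even if uptake and function are unrelated among people treated alike. Reported without qualification, it would add little to the ANCOVA results while looking like evidence of a link within patients.

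A separate problem is that the error rate for these tests cannot be worked out from the text, because neither the governing threshold nor the number of tests is fixed. Correcting for multiplicity does not cure the arm effect, and adjusting for arm does not settle multiplicity.

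**Working it through.** **1. The plan's own figure.** XI.2 gives effect sizes 2.08 and 1.37, significance 0.05 and 80% power. A two-sided two-sample t-test at the smaller value, d = 1.37, needs 9.43 per group, so 10 (power 82.6%). Four groups of 10 give 40, as stated. I use 40 completers: 20 active and 20 sham, 10 per arm. No power or error rate is stated for the correlations.

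**2. Expected size of the artefact.** Assume two equal groups, unit within-arm SD, zero within-arm correlation and a shift d on both changes. The pooled product-moment correlation is

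rho = (d²/4) / (1 + d²/4).

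- d = 0.5: 0.0625 / 1.0625 = 0.06
- d = 0.8: 0.16 / 1.16 = 0.14
- d = 1.37: 0.469 / 1.469 = 0.32
- d = 2.08: 1.082 / 2.082 = 0.52

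The critical value is r = t / √(df + t²). With n = 40 (38 df) it is 2.024 / √(38 + 4.098) = 0.312 at two-sided 0.05, and 2.980 / √(38 + 8.882) = 0.435 at 0.005. A shift near 1.37 SD therefore puts the expected correlation at the 0.05 boundary.

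**3. Simulated rejection rates for one correlation.** Normal data, no within-arm relation, 20,000 or more runs per setting; p<0.05 / p<0.005. The shift is stimulation versus sham in the first column and gait versus balance training in the second.

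| Shift on both (SD) | All arms pooled, 20 v 20 | Active arms only, 10 v 10 |
|---|---|---|
| 0 | 5% / 0.5% | 5% / 0.6% |
| 0.5 | 6% / 0.8% | 6% / 0.7% |
| 0.8 | 14% / 2.5% | 9% / 1.4% |
| 1.0 | 24% / 6% | 14% / 2.6% |
| 1.37 | 58% / 24% | 31% / 8% |
| 2.08 | 98% / 87% | 79% / 41% |

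Mean pooled Spearman rho is 0.33 at 1.37 SD and 0.55 at 2.08 SD.

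**4. After arm adjustment.** Ranks were residualised on arm and then correlated. With the four-level factor and n = 40, rejection is 4.9% to 5.1% at 0.05 and 0.4% to 0.6% at 0.005 at every shift in the table. With the two-level factor in the active arms only, it is 4.9% to 5.3% and 0.5% to 0.6%.

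**5. Number of tests (derived; the plan does not state it).** XI.1 lists 4 + 6 + 7 + 3 = 20 muscles in four groups. VII.E.6 has five walking or balance tests: FGA, T25FW, BBS, posturography and 6MWT. Posturography has 3 measures × 4 conditions = 12, which makes 16 scores with the other four tests.

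- Groups by tests: 4 × 5 = 20
- Muscles by tests: 20 × 5 = 100
- Muscles by all scores: 20 × 16 = 320; with three SUV versions, 960

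At 0.005 uncorrected, expected false positives are 20 × 0.005 = 0.1, 100 × 0.005 = 0.5 and 960 × 0.005 = 4.8. The chance of at least one is 1 − 0.995^m: 9.5%, 39.4% and 99.2%. These chances assume independent tests, so correlated muscles would lower them; the expected counts would not change.

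**6. The two threshold rules differ.** Bonferroni at 0.05 equals 0.005 per test for 10 tests. For 20 tests it is 0.0025, and for 960 it is 0.00005. Bonferroni does not remove the arm effect: at 0.05/100 = 0.0005, the pooled test still rejects in 7.6% of runs at 1.37 SD, against 0.05% nominal.

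**The case against.** **The correlation may use the active arms only.** The wording about change after ctDCS and training allows that reading, and it removes the stimulation-versus-sham route completely. This stands as an ambiguity. It does not clear the plan, because I.5 also expects gait training plus tDCS to do best, and a training difference acts in the same way, though less strongly (second column of the table).

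**The effect sizes are not tDCS effects on FDG.** This stands. A reader might infer that the plan's own figures imply a 58% error rate. They do not. XI.2 attributes 1.37 to the study that VII.E.6 names as the basis of the balance training, and both active and sham arms receive training. No effect size for FDG change appears anywhere. At 0.5 SD the inflation is slight.

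**Multiplicity may already be handled.** A reader might infer that about 100 correlations are run with no correction and that 0.005 is the only threshold. The documents do not support that. The Bonferroni sentence is in the same section and could be meant to cover the correlations, in which case the multiplicity concern largely falls away. The figure of 100 assumes muscle-by-muscle testing; XI.1 calculates SUVs per muscle but does not say that correlations are run per muscle.

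**The label on the 0.005 rule may be deliberate.** V.8 lists brain and spinal cord as well as muscle among the tissues to be evaluated. XI.1 describes only leg-muscle uptake, so the rule's scope needs clarifying. It should not be assumed to be a slip for leg muscle.

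**A pooled correlation is not strictly a false positive.** If tDCS shifts both measures, they are associated in the pooled sample, and the plan claims only that they are related, not that one drives the other. This is right, and it makes the problem one of interpretation. The unadjusted test still cannot separate that association from a relation among people treated alike.

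**Conclusion.** The point holds in a limited form. The correlation has no arm term and no stated population, and under the trial's own hypotheses arm differences alone can make it significant. The size depends on an effect the documents do not supply: close to nominal at 0.5 SD, roughly two to three times nominal at 0.8 SD for p<0.05 with all arms pooled, and dominant at the large effects used for sample size. These figures assume normal changes, equal shifts on both measures, 40 completers, two-sided tests, and an FDG variable that stimulation or training affects. The hypothesis concerns symmetry, so the mechanism applies most directly to the asymmetry index.

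On multiplicity, the defect is two unreconciled threshold statements and an undefined family of tests, not a demonstrated absence of correction. The whole point bears on the supporting claim about mechanism and leaves the ANCOVA comparison of arms untouched. It should be corrected before analysis.

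**What to change.** In section XI.1:

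- State whether the correlation uses all four arms or only the active arms, and which functional visit defines the change (FDG is measured only at Sessions 2 and 12).
- Use a partial Spearman correlation adjusted for randomised arm: a four-level factor if all arms are used, two-level if only the active arms are.
- Reconcile the two threshold statements into one rule for the leg-muscle correlations, and say what the brain-imaging threshold covers, if anything.
- Define the family of tests in advance, for example the asymmetry index of the four muscle groups against a named set of walking and balance scores. The correction method and the exact list are for the authors to choose.
- Report these correlations as exploratory.

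The cost is SAP wording, with no extra participants, visits or scans. The four-arm adjustment uses three degrees of freedom (38 to 35), which raises the critical correlation at 0.05 from 0.312 to 2.030 / √(35 + 4.121) = 0.325. Fewer muscle-level tests would be available for formal claims.

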Cerebellar tDCS, gait and balance training in PwMS

PI: [name]
IRB ID #: 201912430

Project Details

I. Project Introduction

I.1 *Project to be reviewed by:*
IRB-01

I.2 *Project Title:*
The effects of 4 mA cerebellar transcranial direct current stimulation combined with gait and balance training in people with multiple sclerosis

I.3 *Short Title (optional):*
Cerebellar tDCS, gait and balance training in PwMS

I.4 *Provide a short summary of the purpose and procedures of the study proposed in this IRB application.*

- **DO NOT include information on studies not proposed in this application.**
- **Use LAY terminology only. This must be easily understandable by IRB community members and nonscientists.**
- **DO NOT cut and paste technical abstracts from funding applications that may not be understood by a general audience.**

The purpose of this study is to investigate the effects of cerebellar transcranial direct current stimulation (tDCS) combined with gait or balance training on glucose uptake in the leg muscles as well as gait and balance performance. We will conduct tDCS or SHAM followed by balance or gait training over 9 days. We will evaluate gait and balance with well-established functional tasks and changes in glucose uptake with PET-FDG imaging.

I.5 *Specify your research question(s), study aims or hypotheses (do not indicate "see protocol")*
Our research question is whether tDCS combined with gait and balance training can improve gait and balance performance as well as increase glucose uptake symmetry in the leg muscles of people with multiple sclerosis. We hypothesize that gait, balance, and glucose uptake symmetry will improve in both groups that received training (gait or balance) combined with tDCS compared to the groups that only receive training (sham tDCS). Moreover, we hypothesize that the greatest improvements will be seen in the gait and tDCS group.

I.6 *Background and significance and/or Preliminary studies related to this project. (do not indicate "see protocol")*

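### XI.1 correlates function with change in FDG uptake rather than change in the asymmetry index, so it can miss a symmetry-function link when the legs converge

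*Combined protocol and SAP*

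**What the plan says.** The research question in I.5 is whether the intervention can "increase glucose uptake symmetry in the leg muscles of people with multiple sclerosis". The hypothesis there is comparative: "We hypothesize that gait, balance, and glucose uptake symmetry will improve in both groups" that receive tDCS with training, relative to sham with training. I.5 gives no direction for absolute uptake. The lay summary in I.4 is broader and says the study will evaluate "changes in glucose uptake with PET-FDG imaging".

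XI.1 sets out the imaging measures. "Standardized uptake values (SUV) based on the injected dose and body weight will be calculated for each muscle". Then "Asymmetry indices (AIs) will be calculated to determine the magnitude of asymmetry in SUVs between the legs", by an equation that is cited but not printed, and "An AI greater than 10% will be considered asymmetric". The next sentence gives the imaging-function analysis, a Spearman correlation to "test whether the change in FDG uptake is significantly related to the change in walking and balance scores after ctDCS and training". It does not say which muscle, which leg, or what combination of legs supplies the uptake change.

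XI.1 also notes that "SUVs may be affected by blood glucose and insulin levels". It plans SUV analyses without normalization and, separately, with values adjusted to a blood glucose of 100 mg/dL and/or referenced to liver. Under VII.E.6, PET is done at Sessions 2 and 12 only.

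**The concern.** Symmetry is a relation between two legs; uptake is a level. A patient can become more symmetric with total uptake rising, falling or unchanged. If the legs move toward each other, the uptake change has opposite signs in the two legs. Its correlation with function then also has opposite signs, and it can vanish if the legs are combined. Variation between scans that scales both legs alike stays in an SUV change but drops out of a relative AI.

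At stake is the only planned analysis that links the PET scans to walking and balance. It could give a null or contradictory answer when greater symmetry does accompany better function. The index suited to the question is already computed, but its only stated use is the 10% classification.

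**Working it through.** **The plan's own figure.** The documents give no power or size for this correlation. The only computed figure is the sample size in XI.2, and it reproduces. A two-sided two-sample t-test with d = 1.37, alpha 0.05 and 80% power needs 9.43, so 10 per group and 4 x 10 = 40; recruitment is 40 x 1.2 = 48. It enters below only as n = 40, taking all completers together.

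**Assumed form of the index.** For SUVs a and b, AI = (a - b) / ((a + b)/2). The relative form is an assumption, since the equation is only cited; a percentage cut-off is consistent with it.

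**Counterexample (arithmetic only).** Let SUVs of 2.0 and 1.6 converge to 1.8 and 1.8.
- Mean uptake: (2.0 + 1.6)/2 = 1.8 before and 1.8 after, so the change is 0.
- AI: (2.0 - 1.6)/1.8 = 22% before and 0 after.
- By leg: -0.2 and +0.2.

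A second case starts every patient at 1.2 and 0.8 and shifts 0.02 to 0.20 from one leg to the other. Mean uptake change is exactly 0 for all, while AI falls by 2 x 0.02/1.0 = 4 points up to 2 x 0.20/1.0 = 40 points. Mean uptake change then carries no information on function, even if function follows AI perfectly.

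**Shared scan factor.** If a factor g multiplies both legs, AI = (ga - gb)/((ga + gb)/2), and g cancels. It does not cancel in ga - a0, where a0 is the baseline SUV.

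**Scenario 1, convergence (all inputs assumed).** Baseline SUVs are 2.0 and 1.6. Each leg moves by c = 0.1 + 0.1z, with z standard normal, so Session 12 gives (2.0 - c)g and (1.6 + c)g. Function = 0.5z + sqrt(0.75)e, with e independent standard normal. g is log-normal with SD s. With n = 40, mean Spearman and power at 0.05 are:

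| Imaging variable | s = 0 | s = 5% | s = 10% | s = 15% |
|---|---|---|---|---|
| Signed AI change | 0.47, 89% | 0.47, 88% | 0.47, 89% | 0.47, 89% |
| Magnitude AI change | 0.40, 77% | 0.40, 75% | 0.40, 75% | 0.40, 75% |
| Two-leg mean uptake | no variation | 0.00, 5% | 0.00, 4% | 0.00, 5% |
| Lower-uptake leg | +0.47, 89% | +0.36, 63% | +0.24, 32% | +0.17, 19% |
| Higher-uptake leg | -0.47, 89% | -0.34, 60% | -0.21, 28% | -0.15, 16% |

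Magnitude loses power because patients with c > 0.2, that is z > 1 or about 16%, pass parity and are folded back. Function was generated from signed convergence, which favours the signed form.

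**Scenario 2, different assumptions.** Baseline AI 25% (SD 6), AI change -10 points (SD 5), correlation 0.7 between AI improvement and function, n = 40.
- Total uptake changes independently of symmetry (SD 8%): mean Spearman is about 0.00 for two-leg mean uptake, 0.20 for the more-affected leg, -0.18 for the less-affected leg and 0.67 for AI change.
- Only the more-affected leg changes: 0.64 for uptake change and 0.67 for AI change.

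**The case against.** Several points on the other side stand.

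- Uptake change is a stated purpose in I.4, so correlating it with function is legitimate in itself. It should be kept, not replaced outright.
- The zero correlation needs a two-leg summary. XI.1 calculates SUVs muscle by muscle and nowhere says that the legs are averaged. It also needs roughly opposite changes in the two legs.
- The plan's glucose and/or liver normalization may remove much of the shared scan variation; how much would remain is unknown. In scenario 1 with s = 0, single-leg uptake does as well as signed AI. With s = 3%, single-leg power is about 77-79%, against about 75% for magnitude AI. Normalization does not, however, remove the opposite signs or the cancellation between legs.
- The correlation sentence directly follows the AI sentences, so the authors may have meant AI change. The text does not say so, and if that was the intent the edit costs nothing.

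A reader might infer that the planned correlation will be null, or that 89% against 5% is the general gain from switching to AI. The documents support neither. They do not say which pattern of change is expected or how the legs are combined, and every simulation input is assumed. A reader might also infer that correlating AI change would test the I.5 hypothesis. It would not: that hypothesis compares stimulation groups, while the correlation concerns only the link between imaging and function.

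**Conclusion.** The point holds in a limited form. The hypothesis is about symmetry, and the imaging-function correlation names uptake. When uptake converges between the legs, uptake change can show no correlation in a two-leg summary, or opposite signs by leg, although better symmetry tracks better function. The counterexample is plain arithmetic and does not rest on the simulations.

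The size depends on the pattern of change. It ranges from near agreement, when only the more-affected leg changes, to complete loss, when legs that converge equally are averaged. Single-leg uptake lies between, according to how much shared scan variation is left. The power figures assume a relative AI, n = 40, a true correlation of 0.5 and a threshold of 0.05. They would be lower at 0.005, which XI.1 states for brain imaging.

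**What to change.** In XI.1:

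1. Name the change in AI from Session 2 to Session 12 as the imaging variable for the symmetry-function correlation, by muscle group, and state which normalization applies.
2. Print the AI equation and say whether it is signed relative to the more-affected leg or a magnitude. A fall in the signed form reads as better symmetry only where the more-affected leg has the lower baseline uptake. The magnitude form avoids that condition but loses some power when patients overshoot parity.
3. Keep change in SUV, reported separately by leg, as a secondary analysis, because I.4 names uptake change as a purpose.
4. For the between-group hypothesis in I.5, add a separate analysis of AI at Session 12 adjusted for baseline AI. The planned ANCOVA does not name AI, and its 2- and 4-week time points have no PET scan.

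The cost is a few sentences in XI.1, best settled before the data are analysed. The AI is already to be computed, so no further scans, visits or patients are needed.
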